3.12 Sample size calculation

The determination of sample size is carried out using G*Power software, version 3.1.9.6 (Universitat Kiel, Germany; February 2020) using the F-test family, Repeated Measure (RM) ANOVA within and within-between interaction sub-options. The type I error (α) and the study power ($1 - \beta$, where β = type II error) are fixed at 0.05 and 0.80, respectively.

Due to scarcity of information from previous literature on paediatric population, we could not use the parameter estimates (standard deviation of the differences, mean differences between pairs) from prior studies as guides for our sample size calculation. However, to circumvent this, we utilise Cohen's guideline on choosing the effect size for this study.⁴⁴ We assumed that the Cohen's d is large ($d = 0.8$) and used this as our effect size. It had been demonstrated by a

previous study on the efficacy of microneedle as a delivery method for 5% lidocaine dental gel (Septodont, UK) that the effect size could be that large, thus justifying our choice of effect size in general.⁴⁵ For objectives 1 and 2, we used the RM-ANOVA within-group comparison sub-option and fix the number of groups and measurements to 1 and 4, respectively. Based on prior guidelines, moderate-to-high correlations between the within-group measurements ($r = 0.7$) are assumed.^{46,47} For non-sphericity correction (ϵ), a value of 0.75 is assumed since the sphericity assumption is rarely fulfilled in practical and actual trial setting due to unequal correlations between measurement pairs and the chosen ϵ value is midway between its lower bound of 0.5 and maximal value of 1 to fairly preserve the RM-ANOVA test against inflated type I error rate (α) when non-sphericity occurs.⁴⁸⁻⁵¹ Hence, for objectives 1 and 2, we require a sample size of 23 subjects. Assuming a 10% attrition (drop-out) rate, the total sample size is 26 ($n_{\text{total}} = 26$).

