3.14 Planned Statistical Analysis

The data will be initially checked and cross-examined with the information in the data collection sheet for accuracy, consistency and the amount of missing data. Missing data will be treated as Missing At Random (MAR) and multiple imputation will be considered to impute the missing values in order to reduce the biasness of the parameter estimates. Any variable with serious missing data problem (more than 40%) will be dropped from further analysis.^{54,55} All patients will be analysed according to the original randomization group, based on the intention-to-treat (ITT) analysis.

All data will be descriptively summarized as mean and standard deviation (SD) for the normally-distributed numerical variables (or median and interquartile range (IQR) for the non-normally distributed numerical variables) and frequency and percentage for categorical variable. For numerical data, the normality assumptions will be evaluated subjectively using the histogram with overlying normal distribution curve, box and whisker plot and steam-and-leaf diagrams and objectively using the Kolmogorov-Smirnov and Shapiro-Wilks tests ($p>0.05$ indicates normal distribution assumption is met). Fisher's coefficient of skewness will be subsequently utilized to assess the severity of skewness in non-normally distributed numerical variables using the following formula:

Fisher's coefficient of skewness: Skewness / standard error of skewness

Any value outside ± 2 range will indicate extreme skewness.⁵⁶

For the first and second objectives, repeated measure ANOVA and generalized mixed effect model (GLMM) with an identity link function will be used to assess and estimate the differences in terms of VAS score means between the periods of interventions, considering intra-subject correlations. For repeated measure ANOVA, Mauchly's test of sphericity will be used to assess the sphericity assumption. If sphericity assumption is violated, the Greenhouse-Geisser correction will be used if $\varepsilon < 0.75$ or the Huynh-Feldt correction if $\varepsilon > 0.75$.⁵⁷ Within-group analysis will be used to assess the significance of mean VAS score differences between treatment pairs. To assess the presence of carryover effect, the within group-between treatment sequence interaction effect will be assessed for statistical significance.

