For GLMM, the Restricted Maximum Likelihood (REML) estimator will be used to estimate the model parameters. The unadjusted and adjusted estimates of the parameters obtained using the GLMM will be examined, with and without the consideration of periodic effects. Random intercept model and robust variance estimators will be used for the calculation of standard errors. Likelihood ratio test will be utilized to compare the nested models and Akaike Information Criteria (AIC) and Bayesian Information Criteria will be used for comparing non-nested models. Multicollinearity between fixed effects (age, sex and treatment effects) will be evaluated using bivariate correlations. Besides, interaction effects (effect modification) between significant fixed predictors will also be assessed by evaluating the significance of interaction terms. Residual diagnostics will also be performed to ensure the validity of model assumptions and the presence of outliers and influential points will be investigated to ensure that they do not influence the model parameter estimates. The presence of any influential point will then be removed or corrected if these are due to measurement errors or wrong data entry or retained if the values are authentic. We will also carry out sensitivity analyses to investigate the effects of missing data under the Missing At Random (MAR) framework.

For the third and fourth objectives, the correlation between VAS pain score and PainMonitor™ device is tested using Pearson correlation coefficient if both VAS pain scores and PainMonitor™ device are normally distributed (Gaussian) and Spearman coefficient will be used if at least one pain scores (obtained by either measuring modality) are not normally distributed. Intraclass correlation coefficient (ICC) will be computed to assess the agreement between the VAS scores obtained using the two different modalities (VAS pain score vs PainMonitor™ device) and the results will be interpreted according to the Koo-Li criteria.⁵⁸ The Bland and Altman (B&A) plot will be obtained to further assess the agreement between the two scores. The limits of agreement obtained will be assessed to ensure there is an acceptable agreement between the pain measurement modalities.

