For each analysis, the significant threshold for p value is fixed at 0.05 and 95% confidence interval (CI) will be obtained for each parameter estimates. Data analysis will be performed using Statistical Package for Social Science (SPSS™) (IBM Corp. Released 2020. IBM Statistics for Windows, Version 27.0, Armonk, NY: IB Corp) and STATA™ version 15 (StatCorp. 2017. Stata Statistical Software: Release 15. College Station, Texas: StataCorp LP).

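### The mixed model takes robust standard errors from only 23 to 26 children with no small-sample correction, so its Wald test of the four arms would exceed 5% and its 95% intervals would be somewhat too narrow

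*Combined protocol and SAP*

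**What the plan says.** Section 3.14 plans two analyses of the four-arm comparison for objectives 1 and 2: "repeated measure ANOVA and generalized mixed effect model (GLMM) with an identity link function will be used". Neither is called primary.

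For the mixed model, "the Restricted Maximum Likelihood (REML) estimator will be used to estimate the model parameters", and the models are to be examined "with and without the consideration of periodic effects". On standard errors the text is: "Random intercept model and robust variance estimators will be used for the calculation of standard errors". At the end of the section, "the significant threshold for p value is fixed at 0.05 and 95% confidence interval (CI) will be obtained for each parameter estimates".

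Section 3.12 fixes the number of children: "Hence, for objectives 1 and 2, we require a sample size of 23 subjects". With 10% attrition the total is 26. That figure is derived for the repeated-measures ANOVA, with one group, four measurements and a non-sphericity value of 0.75.

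Section 3.14 names SPSS and Stata. It does not say which degrees of freedom, small-sample factor or reference distribution go with the robust standard errors.

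**The concern.** A robust (sandwich) variance is built from the residuals of the independent clusters, which here are the children. With few clusters it is biased downwards. A joint test of three treatment parameters adds a second problem: it uses a 3×3 covariance matrix estimated from about 25 children, and a chi-square reference treats that matrix as known. REML does not repair this, because it concerns the variance components and not the sandwich.

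Hypotheses 2.4.1 and 2.4.2 each claim at least one difference among the four arms. A liberal joint test would support them too often when the preparations do not differ. The microneedle-versus-control differences from the mixed model, which are the estimates a reader would use, would carry intervals that cover less than the promised 95%.

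**Working it through.** **Inputs.** From 3.12: n = 23 evaluable and 26 enrolled, 4 measurements (so 3 treatment df), alpha 0.05, power 0.80, d = 0.8, r = 0.7, epsilon 0.75. From 3.14: robust variance, p threshold 0.05, 95% intervals.

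**1. The plan's own figure.** Take f = d/2 = 0.4, df1 = 3 × 0.75 = 2.25 and df2 = 3(n-1) × 0.75. The noncentrality is f² × n × 4 × 0.75, which at n = 23 is 0.16 × 23 × 4 × 0.75 = 11.04. The noncentral F then gives power 0.815 at n = 23, and 23/0.9 = 25.6, rounded up to 26. The planned numbers are reproduced. (They are reproduced on this route only if r = 0.7 is left out; dividing the noncentrality by 1 - 0.7 gives n = 8. That is a separate matter.)

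**2. Exact size of the joint robust test.** With complete data and treatment terms only, the estimates are differences of arm means. The uncorrected sandwich equals (n-1)/n times the usual unbiased covariance. Hence

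- W = T² × n/(n-1), where T² is Hotelling's statistic;
- T² = [3(n-1)/(n-3)] × F(3, n-3) under no difference, for any within-child covariance.

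With the chi-square critical value 7.815, rejection means F(3, n-3) > 7.815 × (n-3)/(3n):

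- n = 26: 7.815 × 23/78 = 2.304, probability 10.4%;
- n = 23: 7.815 × 20/69 = 2.265, probability 11.2%.

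The same formula with other references:

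| Reference for the 3-df test | n = 26 | n = 23 |
|---|---|---|
| Chi-square, uncorrected | 10.4% | 11.2% |
| Chi-square, n/(n-1) factor | 9.4% | 10.1% |
| F, residual df 4n-4, uncorrected | 9.5% | 10.2% |
| F, residual df, n/(n-1) factor | 8.7% | 9.2% |
| F(3, n-1), uncorrected | 7.3% | 7.7% |
| F(3, n-1), n/(n-1) factor | 6.6% | 6.8% |

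**3. With period terms** (simulation, 20,000 null trials per setting, normal data, r = 0.7, chi-square reference, uncorrected): 11.7% (n = 26) and 12.7% (n = 23). Adding a time-varying covariate gives 12.1% and 12.8%.

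**4. Single contrasts and intervals, treatment-only.** The rejection rate with 1.96 is P(|t(n-1)| > 1.96 × √((n-1)/n)).

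- 1.96, uncorrected: 6.6% (26) and 6.8% (23).
- 1.96 with the n/(n-1) factor: 6.1% and 6.3%.
- t(n-1) without the factor: 5.4% and 5.5%, so coverage is about 94.5%.
- Width with 1.96 relative to the correct t(n-1) interval: 0.933 and 0.924 uncorrected, 0.952 and 0.945 with the factor. The intervals are about 5 to 8% too short.

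With period terms, 1.96 and no correction, simulated single contrasts reject 7.1% (26) and 7.7% (23). Coverage with 1.96 is therefore about 92 to 94% overall.

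**5. Alternatives, same simulations.** A Hotelling-type reference with 3 and n-3 df gives 4.9 to 5.1% without period terms, 5.7% with them, and 6.1 to 6.2% with a time-varying covariate as well. The model-based F from a random-intercept fit, without the sandwich, gives 4.8 to 5.2% under equal correlations. It gives 6.7% in one unequal case with period terms (n = 23, correlation 0.85 to the power of the lag).

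**The case against.** The strongest reply is that the plan names no Wald test and no chi-square reference. Robust variance is specified only for standard errors. Two joint procedures are named in 3.14, and neither uses a sandwich: the repeated-measures ANOVA with Greenhouse-Geisser or Huynh-Feldt correction, and a likelihood ratio test for nested mixed models. With complete normal data and treatment terms only, the Greenhouse-Geisser ANOVA runs at 4.1 to 4.4% under equal correlations and 4.8% under the unequal pattern above. A maximum-likelihood ratio test from a random-intercept model runs at 5.6 to 5.7% and 7.4 to 7.5%. The ANOVA is listed first and is the test the sample size rests on.

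Most of this stands, and it limits the point. A reader might infer that the trial's four-arm test has twice its stated error rate. The documents do not support that: the ANOVA is also a four-arm test and is unaffected, and the doubling depends on a reference the plan does not state. A reader might also infer that every interval in the trial is too narrow. Only mixed-model intervals are affected, and modestly.

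What the reply does not remove is the stated rule itself. Neither the ANOVA nor the likelihood ratio test repairs the mixed-model standard errors and 95% intervals that 3.14 promises. Adjusted estimates, with and without period, are planned only in the mixed model. With no primary analysis named, the liberal result could be the one cited if the two disagree.

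**Conclusion.** The point holds for the mixed model only. Following the robust-variance sentence with 23 to 26 children gives liberal inference under every conventional reference examined: about 9 to 11% for the 3-df Wald test with chi-square or residual df, about 12 to 13% with period terms and chi-square, and 6.6 to 7.7% with n-1 df in the treatment-only model, against 5%. The interval shortfall is smaller: about 92 to 94% coverage with 1.96, and about 94.5% with t(n-1) and no factor in the treatment-only model.

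The treatment-only results are exact for complete normal data and do not depend on the correlation. The period-term results are simulated at r = 0.7. Which figure applies depends on a choice the plan leaves open. This should be amended before analysis, but it does not undermine the ANOVA or the trial as a whole.

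**What to change.** In 3.14, make two changes.

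1. Name one primary analysis for objectives 1 and 2.
2. Replace the robust-variance sentence with model-based REML inference: fixed treatment and period, a within-child covariance that allows unequal correlations (for example unstructured), and Kenward-Roger degrees of freedom for all mixed-model tests and intervals.

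Dropping the sandwich while keeping a plain random intercept is not enough. Section 3.12 itself expects unequal correlations, and the model-based F reached 6.7% in such a case. If a sandwich variance is kept, use a bias-reduced version (CR2) with Satterthwaite or Hotelling-type degrees of freedom.

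The cost is a short amendment, mixed-model intervals about 5 to 8% wider, and more covariance parameters: an unstructured 4×4 matrix has 4 × 5/2 = 10, against 2 for a random intercept. The exact proposed model was not simulated here. The nearest check is the Hotelling-type reference, at 4.9 to 5.1% without period terms and 5.7% with them. No change to the number of children is needed for this point.

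### All planned missing-data sensitivity analyses stay under MAR, so they cannot show whether missingness tied to unrecorded pain changes the result; the 40% deletion rule does not exempt outcomes.

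*Combined protocol and SAP*

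**What the plan says.** Section 3.14 (Planned Statistical Analysis) sets the main assumption: "Missing data will be treated as Missing At Random (MAR) and multiple imputation will be considered to impute the missing values". Later in the section, after the mixed-model description, the plan promises "sensitivity analyses to investigate the effects of missing data under the Missing At Random (MAR) framework". No delta-adjusted, tipping-point, pattern-mixture or worst-case analysis is named anywhere.

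The same section adds: "Any variable with serious missing data problem (more than 40%) will be dropped from further analysis". It does not exempt the VAS or PainMonitor outcomes.

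Section 3.12 gives the expected loss: "we require a sample size of 23 subjects", and then "Assuming a 10% attrition (drop-out) rate, the total sample size is 26".

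Three other places bear on the point:
- Section 3.10.3 keeps withdrawn participants under follow-up for outcomes and in the intention-to-treat analysis.
- Section 3.9.2 separates the four visits by at least three weeks.
- Section 3.9.3 takes the outcome VAS one minute after cannulation, at the visit itself.

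**The concern.** Observed data cannot separate MAR from missingness that depends on the unseen value. A set of analyses that all assume MAR therefore leaves that assumption untested, however many methods are compared.

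The untested case is plausible here. The outcome is a child's own pain rating straight after cannulation, and section 1.1 says that fear of needles may be worse in children who are cannulated regularly. A child may refuse, may be too distressed to use the slider, may have a failed cannulation, or may stay away expecting pain. In each case no score exists, and its absence may depend on what it would have been. Only the microneedle conditions break the skin before the cream goes on (section 3.9.2), so this kind of loss could differ between arms. If high scores go missing mainly at microneedle visits, the error favours the new device.

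The 40% rule is a second, smaller gap. Applied literally to an outcome, it would discard that outcome instead of analysing the visits that were observed.

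**Working it through.** **Inputs from section 3.12.** 23 evaluable children, 10% attrition, 26 in total, four measurements per child, within-child correlation r = 0.7, d = 0.8. The documents give no VAS standard deviation and no drop-out pattern, so departures from MAR below are assumptions shown as a range.

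**The plan's own figure.** 23 / (1 − 0.10) = 25.6, rounded up to 26. This reproduces, and 26 − 23 = 3 expected drop-outs. (The 23 does not follow from the stated ANOVA inputs: the usual noncentral-F formula gives 8 at f = 0.4 and 4 at f = 0.8. That is a separate matter and does not affect this point.)

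**Shift in an arm mean.** Shift = (share of scores missing in the arm) × (departure from MAR). In a balanced crossover, a child who leaves after visit 2 has missed any given arm with probability 1/2, so 3 such children give 1.5 missing scores per arm on average.

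| Departure | 3 of 26 missing in the arm (the most that 3 drop-outs allow) | 1.5 of 26 (all leave midway) |
|---|---|---|
| 10 mm | 1.2 mm | 0.6 mm |
| 20 mm | 2.3 mm | 1.2 mm |
| 30 mm | 3.5 mm | 1.7 mm |

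A contrast with control moves by the full amount only if the control arm has no such departure. If the departure is the same in both arms, the contrast moves by departure × (difference in missing shares), which is zero when the shares are equal.

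**Against the precision of a contrast, in SD units.** SE = √(2 × (1 − 0.7) / 23) = 0.16 SD; the 95% half-width is 1.96 × 0.1615 = 0.32 SD (normal approximation). With 3 of 26 missing, departures of 0.5, 1, 1.5 and 2 SD give shifts of 0.06, 0.12, 0.17 and 0.23 SD.
- For an observed contrast of 0.8 SD to lose significance, the departure would have to be (0.80 − 0.32) / (3/26) = about 4.2 SD. To remove the contrast entirely, it would have to be 0.80 / (3/26) = about 6.9 SD.
- For a contrast near 0.32 SD, a shift of 0.12 SD is more than a third of the estimate.

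**Simulation.** 26 children on the 24 sequences, total SD 1, r = 0.7, random-intercept model with period effects, 1,500 trials per row. The mechanisms are assumptions. The contrast is one microneedle arm against control, nominal level 5%.

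| Mechanism | Scores missing | True difference | Result |
|---|---|---|---|
| Drop-out after a recorded high score (MAR) | 6–11% | 0 | bias about 0, rejection 4–5% |
| High scores unrecorded, microneedle visits only | 7.5% | 0 | bias −0.09 SD, rejection 8% |
| High scores unrecorded, microneedle visits only | 15% | 0 | bias −0.19 SD, rejection 16.5% |
| High scores unrecorded, all arms | 10–20% | 0 | bias about 0 |
| High scores unrecorded, all arms | 16% | 0.8 SD | estimate 0.64 SD |
| High scores unrecorded, all arms | 27% | 0.8 SD | estimate 0.58 SD |

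**The 40% rule.** 40% of 26 is 10.4, so at least 11 scores must be missing in one condition. The binomial probability is about 0.00002 at 10% missing, 0.8% at 20% and 12.5% at 30%. This assumes that losses are independent.

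**The case against.** The other side has four good arguments.

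1. **Stopping after a painful visit.** A reader might infer that any child who leaves after a painful visit breaks the analysis. The documents do not support that. The VAS is recorded at that visit, so drop-out that depends on it is MAR; the REML mixed model in section 3.14 uses it, and the simulation shows no bias. This argument stands in full and confines the point to pain that was never recorded.

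2. **MAR comparisons are informative.** A reader might conclude that the planned sensitivity analyses are empty. They are not. Repeated-measures ANOVA without imputation uses complete cases, so comparing it with imputed or mixed-model results tells something. It does not test MAR itself.

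3. **The plan limits missing data.** Section 3.10.3 follows withdrawn participants, section 3.4 enrols children who attend regularly, section 3.9.3 has a trained nurse helping with the scale, and section 3.11 has the case report forms checked fortnightly. These deserve credit and lower the expected loss. But a score exists only if the child receives that visit's patch, cream and cannulation, so follow-up cannot supply one for a condition never given.

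4. **The size is small.** Three missing scores in one arm with none shifted in control is the extreme case. One can make the effect look large by starting from a p-value just under 0.05 and choosing a VAS standard deviation, but the documents supply neither. The table's first column is therefore a ceiling for the planned attrition.

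On the 40% rule, a reader might infer that the skin-conductance and agreement objectives are likely to be lost. At 10% attrition that is very unlikely. The budget lists one PainMonitor, and an outage would break the independence assumption, but a budget line is not evidence of failure.

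**Conclusion.** The gap is real and limited. As written, the plan cannot show whether missingness related to unrecorded pain alters the comparison of arms. With the planned 3 of 26 drop-outs, the arm mean moves by at most 1.2 to 3.5 mm for assumed departures of 10 to 30 mm, and by about half that if they leave midway.

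A reader might infer that the trial's main finding is at risk. Reading the plan's d = 0.8 as 0.8 SD between two conditions, it is not: such an effect would survive any plausible departure. Smaller contrasts could be affected, chiefly if the loss is concentrated in the microneedle arms.

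The 40% rule is a drafting gap. Its literal effect on an outcome is clear, and its chance of being triggered at the planned attrition is negligible under independent losses.

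**What to change.** In section 3.14:

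1. Keep the MAR analyses and add a prespecified delta-adjusted (tipping-point) analysis. Impute missing VAS scores under MAR, then add 0 to 30 mm to the imputed values, once in all arms and once in the microneedle arms only. For each of the three microneedle-versus-control contrasts, report the delta at which the conclusion changes, or state that none in the range does so.
2. Restrict the 40% deletion rule to covariates, and state that VAS and PainMonitor outcomes are always analysed on the observed visits.

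The cost is a few sentences of SAP wording and a little more analysis. No further participants, visits or measurements are needed.

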1.6 Problem statements and justifications of the research

Based on our brief review of literature, there are two problem statements summarising the identified research gaps that justify the conceptual significance of this research:

- i) The combined effects of microneedle usage reduce the dose and hasten the action of EMLA Cream on skin anaesthesia in paediatric patients requiring venous cannulation for regular blood transfusion have not been properly elucidated in previous studies. This study aimed to demonstrate a better care for paediatric patients that frequently receive blood transfusion as part of the management of their clinical conditions.
- ii) The agreement between VAS score and the physiological skin conductance algesimeter index obtained using medical devices has not been previously investigated in paediatric patients. This study aimed to highlight the potential of physiological pain monitoring in critical and semi-critical care where the patient is often either semi-conscious or unconscious.

Hence, it is anticipated that our research findings may satisfactorily provide the answers to the problem statements above, resulting in significant application of microneedle in TDS of drugs such as EMLA Cream, and the use of physiological monitoring of pain in paediatric patients. The conceptual framework (**Figure 3**) diagrammatically summarizes our research underpinnings, postulates and justifications.

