For objective 2, we could not calculate the sample size since we don't have the estimate of the standard deviation of the differences (denoted by (s) henceforth) between the two methods for pain evaluation (the VAS score and the skin conductance algesimeter index obtained via PainMonitor™). Information on (s) is required since the sample size formula for evaluating limit of agreement require s parameters to be explicitly specified. However, we could roughly assess the precision of the limit of agreements (as per (s) magnitude) based on the sample size proposed for objective 1 and 2 using the formula recommended by the original authors.⁵² Based on Bland and Altman (1986), the 95% CI of limit of agreement is given by:

$$\pm 1.96 * \sqrt{3/n} * s^{52},$$

where s = standard deviation of the differences between VAS score and the skin conductance algesimeter index. If we assume a sample size of 24, then the precision of the limit of agreement is:

$$\pm 1.96 * \sqrt{3/26} * s = \pm 0.67 * s,$$

which we deem a satisfactory precision in our case.

However, due to absence of an estimate of (s) from prior studies, the actual precision could not be accurately estimated, thus highlighting the importance of (s) in the actual sample size calculation. Thus, it is hoped the estimate of (s) obtained from this study will be used as a guide for calculating a sample size for a future follow-up study that can answer this study objective more reliably. However,

Hence, the biggest overall sample size required for this study is 26 ($n_{\text{total}} = 26$).

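### Objective 3 does not say how each child's four VAS/PainMonitor pairs enter the correlation, ICC and Bland-Altman analyses, and does not separate within-child tracking from between-child differences

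*Combined protocol and SAP*

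**What the plan says.** Section 3.1 describes a crossover in which each child is assigned a sequence of four treatments, and section 3.9.3 records one VAS score after each cannulation. For objectives 1 and 2, section 3.12 tells the software to "fix the number of groups and measurements to 1 and 4, respectively" and states that "moderate-to-high correlations between the within-group measurements ($r = 0.7$) are assumed". Section 3.14 allows for this correlation in those two objectives, through repeated-measures ANOVA and a random-intercept model.

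For the VAS/PainMonitor comparison (objective 2.2.3, which section 3.14 calls the third and fourth objectives), the plan is that "the correlation between VAS pain score and PainMonitor™ device is tested using Pearson correlation coefficient" if both measures are normal, otherwise Spearman. An ICC of unstated form and a Bland-Altman plot follow. None of these is given in a repeated-measures version, and no unit of analysis is named. Section 3.14 adds: "For each analysis, the significant threshold for p value is fixed at 0.05", with a 95% confidence interval for each estimate.

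On precision, section 3.12 explains that "Information on (s) is required since the sample size formula for evaluating limit of agreement require s parameters to be explicitly specified", and then gives ±0.67s for a limit of agreement. Section 1.6 says the comparison is meant to "highlight the potential of physiological pain monitoring in critical and semi-critical care".

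**The concern.** Four pairs from one child are not four independent observations. Ordinary Pearson, Spearman and Bland-Altman intervals assume that they are. A single coefficient over all pairs also mixes two questions: whether children who report more pain have a higher index, and whether the index rises when the same child has more pain. A monitoring use depends at least partly on the second.

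At stake are the p-value and confidence intervals reported for objective 3, and what they are taken to mean. A device that tracks pain well within a child could be dismissed. One that only separates high scorers from low scorers could be endorsed. Because the unit of analysis is open, it could also be chosen after the data are seen.

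**Working it through.** **Inputs.** Children n = 26 (3.12: 23 plus 10% attrition). Pairs per child m = 4 (3.1, 3.9.3), so 26 × 4 = 104 pairs. Section 3.13 can be read as two outcome times per visit, so four is the count implied by 3.9.3. Alpha is 0.05 (3.14), taken as two-sided because the plan does not say. Within-child correlation ρ is 0.7 for repeated measurements (3.12). No value is given for the paired differences, so 0.3 to 0.7 is an assumed range. Simulations used 10,000 trials of 26 × 4 normal pairs with no treatment effect.

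**1. The plan's own figure.** 1.96 × √(3/26) = 0.666, which reproduces ±0.67s. The sentence before it names a sample of 24, which would give 1.96 × √(3/24) = 0.693. The figure therefore describes 26 independent differences, one per child.

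**2. Correlation test if all pairs are pooled.** With no true association and the same ρ in both measures, the variance of the pooled coefficient is inflated by D = 1 + 3ρ². The approximate type I error is 2 × [1 − Φ(1.96/√D)].

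| ρ | D | Formula | Simulated Pearson | Simulated Spearman |
|---|---|---|---|---|
| 0.3 | 1.27 | 0.082 | 0.083 | 0.083 |
| 0.5 | 1.75 | 0.138 | 0.137 | 0.129 |
| 0.7 | 2.47 | 0.212 | 0.215 | 0.201 |

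Repeat simulations put the Pearson value at ρ = 0.7 between 21% and 22%. A within-child (repeated-measures) correlation test held 4.8% to 5.2% in the same data.

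**3. Limits of agreement if all pairs are pooled.** Putting 104 into the plan's formula gives 1.96 × √(3/104) = 0.333s. With clustering, the squared standard error of a limit, in units of s², is

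(1 + 3ρ)/104 + 1.96² × (1/4) × (1/16) × [2(1 + 3ρ)²/25 + 18(1 − ρ)²/78].

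At ρ = 0.7: 3.1/104 = 0.0298. The bracket is 0.7688 + 0.0208 = 0.7896, and 3.8416 × 0.7896/64 = 0.0474. The sum is 0.0772, and 1.96 × √0.0772 = 0.545.

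| ρ of differences | Correct half-width | Ratio to 0.333s | Simulated coverage of the pooled 95% interval |
|---|---|---|---|
| 0.3 | 0.404s | 1.21 | 89% |
| 0.5 | 0.470s | 1.41 | 83% |
| 0.7 | 0.545s | 1.64 | 76% |

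The coverage runs used the t quantile in place of 1.96. The limits themselves barely move: the pooled SD is √[(104 − (1 + 3ρ))/103] of the true SD, which is 0.996, 0.993 and 0.990. The simulated mean SDs were 0.992, 0.989 and 0.984. The limits are therefore at most about 1% to 2% narrow.

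**4. Other readings of section 3.14.**
- *Child means.* The correlation test holds its level (5.0% to 5.3%). The SD of the differences shrinks to √[(1 + 3ρ)/4] of the single-reading value: 0.69, 0.79 and 0.88. The limits are too narrow for a single reading.
- *By treatment, 26 pairs each.* Each test holds 5%, but there are four results and no rule for combining them. If the tests were independent, the chance of at least one false positive would be 1 − 0.95⁴ = 18.5%. Simulation gave 16% to 18%.

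**5. What a pooled coefficient means.** With ρ = 0.7 in both measures, pooled r = 0.7 × r(between) + 0.3 × r(within).
- Between 0.6, within 0: r = 0.42, naive p = 0.000009.
- Between 0, within 0.6: r = 0.18, naive p = 0.07.

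Equal strengths of association on the two levels lead to opposite conclusions.

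**The case against.** A reader might infer that the plan will pool 104 pairs and report p-values and limits that are too optimistic. The documents do not support that. No section says the pairs will be pooled, and the only n put into the formula for this objective is 26, which points away from pooling. The ±0.33s half-width appears nowhere in the plan. The stated ±0.67s is wider than the correct ±0.40s to ±0.55s for four clustered pairs per child, so it errs on the safe side. Even under pooling it is the confidence intervals that fail, not the limits.

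The sizes also rest on assumptions. The 0.7 in section 3.12 comes from general guidelines rather than trial data, and at 0.3 the type I error is only 8%. The stated objective is agreement, so a test against zero correlation is secondary.

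Nor do the documents require within-child correlation to come first. Section 1.6 concerns patients who are semi-conscious or unconscious, where a reading may have to be interpreted without self-report, and that also depends on between-patient agreement. Visits at least three weeks apart are a limited test of real-time monitoring.

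All of this stands, and it makes the finding conditional. It does not close the gap: each available reading has a defect, and none separates the two levels.

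**Conclusion.** The point holds as an unstated unit of analysis with conditional consequences. Under pooling, the type I error is about 8% to 22% for ρ of 0.3 to 0.7 in both measures, and coverage of the interval for a limit of agreement is about 89% to 76% over the same assumed range for the differences. Under averaging, single-reading limits shrink to 0.69 to 0.88 of their proper width. By-treatment analysis leaves four uncombined results. Within-child tracking is not isolated under any of them.

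The figures assume 26 children with four complete pairs, normal data, no treatment effect and a two-sided test. The plan should be corrected before analysis, but the trial's main conclusion does not depend on it: the primary endpoint is VAS, objectives 1 and 2 already allow for repeated measurements, and section 3.12 treats the agreement results as preliminary to a later study.

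**What to change.** In section 3.14, state that objective 3 uses all post-cannulation pairs with child in the model, and then:

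- Report the within-child correlation (repeated-measures correlation, or a bivariate mixed model with child random effects and arm and visit as fixed effects) and the between-child correlation separately. Neither has to be ranked first.
- Once both measures are on a common scale, take the limits of agreement from a mixed model of the differences, with SD = √(between-child variance + within-child variance). State the form of the ICC on the same basis.
- Obtain confidence intervals by resampling children, not pairs.
- In section 3.12, restate the precision for four pairs per child over a range of within-child correlations (for 26 children, about ±0.40s at 0.3 to ±0.55s at 0.7). Use one consistent n, since the text says 24 and the formula uses 26.

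The cost is analysis text and somewhat more analysis work, with no new data. The intervals will be wider than under naive pooling.
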